4.2.1.3 Primary Analysis of ADA

A summary of the number and percentage of participants who developed detectable ADA to AZD7442 (ADA results to AZD8895 and AZD1061 will be reported separately) by ADA categories (Section 4.2.1.2) in different treatment arms will be presented based on the ADA evaluable analysis set. ADA assessments collected post-dose on the days of IMP administration will be excluded. In addition, descriptive statistics of the maximum titer will

be presented by ADA category. ADA results and titers will be summarized by visit and treatment group.

ADA results will be listed for all participants in the Safety Analysis Set regardless of ADA-evaluable status. ADA titer will be presented, and neutralizing ADA data may be presented for samples confirmed positive for the presence of ADA to AZD7442. AEs in ADA positive participants by ADA positive category will be listed.

The effect of ADA on PK, and safety will be examined by descriptive summaries, if data allow. Descriptive summaries of PK concentration on participants in both the ADA evaluable analysis set and PK analysis set, number of participants having AEs in different categories, and number of participants with AEs by System Organ Class (SOC) and preferred term (PT) will be provided by ADA response: Treatment-emergent ADA positive, non-treatment emergent ADA positive, and ADA negative, and by treatment groups.

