Week (Month)	-	-	1	4	13 (3M)	14	17 (4M)	26 (6M)	27	30 (7M)	39 (9M)	40	52 (12M)	53	65 (15M)	
Window (days)	-	-	± 3	± 5	± 7	± 3	± 5	± 7	± 3	± 5	± 7	± 3	± 7	± 3	± 15	
P = In-Person Visit RTM = Remote TM Visit ^m	P	P	RTM/ P ^m	P	P	RTM/ P ^m	P	P	RTM/ P ^m	P	P	RTM/ P ^m	P	RTM/ P ^m	P	
Coagulation (predose on days of IMP administration)		X			X			X			X		X		X	8.2.4
FSH (suspected postmenopausal women, < 50 years) ^c	X															5.3, 8.2.4
Nasopharyngeal samples																
Documented negative SARS-CoV-2 RT-PCR test from NP specimen taken ≤ 3 days before Day 1 ^d OR SARS-CoV-2 rapid antigen test (local laboratory)	X ^e															8.2.4
SARS-CoV-2 RT-PCR (central laboratory) (predose)		X ^f														8.2.4

Table 1 Schedule of Activities: Treatment Period – Arm A (AZD7442 Q3M)

Period	Screen ^a	Treatment (Days 1-456)													EoT	For details, see Section
Day (* = IMP dosing day)	-7 to 1	1*	8	29	92*	99	121	183*	190	212	274*	281	365*	372	456	
Week (Month)	-	-	1	4	13 (3M)	14	17 (4M)	26 (6M)	27	30 (7M)	39 (9M)	40	52 (12M)	53	65 (15M)	
Window (days)	-	-	± 3	± 5	± 7	± 3	± 5	± 7	± 3	± 5	± 7	± 3	± 7	± 3	± 15	
P = In-Person Visit RTM = Remote TM Visit ^m	P	P	RTM/ P ^m	P	P	RTM/ P ^m	P	P	RTM/ P ^m	P	P	RTM/ P ^m	P	RTM/ P ^m	P	
Urine samples																
Pregnancy test – urine (WOCBP only) ^g ; (predose on days of IMP administration)	X	X ^h		X	X		X	X		X	X		X		X	5.3, 8.2.4, 8.3.9.1
Urinalysis (predose on days of IMP administration)		X			X			X			X		X		X	8.2.4
PK, PD, ADA assessments																
Serum sample for AZD7442 PK assessment (predose on days of IMP administration unless otherwise noted)		D3 (±1d) ⁱ	D11 (±3d) ^j	X	X		X	X		X	X		X		X	8.5.1
Serum sample for AZD7442 ADA assessment (predose on days of IMP administration)		X		X	X		X	X		X	X		X		X	8.5.2.1

Table 1 Schedule of Activities: Treatment Period – Arm A (AZD7442 Q3M)

Period	Screen ^a	Treatment (Days 1-456)													EoT	For details, see Section
Day (* = IMP dosing day)	-7 to 1	1*	8	29	92*	99	121	183*	190	212	274*	281	365*	372	456	
Week (Month)	-	-	1	4	13 (3M)	14	17 (4M)	26 (6M)	27	30 (7M)	39 (9M)	40	52 (12M)	53	65 (15M)	
Window (days)	-	-	± 3	± 5	± 7	± 3	± 5	± 7	± 3	± 5	± 7	± 3	± 7	± 3	± 15	
P = In-Person Visit RTM = Remote TM Visit ^m	P	P	RTM/ P ^m	P	P	RTM/ P ^m	P	P	RTM/ P ^m	P	P	RTM/ P ^m	P	RTM/ P ^m	P	
Serum sample for SARS-CoV-2 nAbs assessment (predose on days of IMP administration)		X		X	X		X	X		X	X		X		X	8.5.3.1

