3.3.2 Visit Window

A windowing convention will be used to determine the analysis value for a given study visit for visit-based assessments, which are as follows:

- Serum sample for SARS-CoV-2 serology (anti-nucleocapsid testing)
- Serum sample for AZD7442 PK assessments
- Serum sample for AZD7442 ADA
- Serum sample for SARS-CoV-2 nAbs levels (pharmacodynamics [PD])
- Serum sample exploratory biomarkers
- Nasal lining fluid sample for AZD7442 PK assessments
- Clinical chemistry, hematology, coagulation, and urinalysis
- Vital signs
- Electrocardiogram (ECG)
- Illness visits for COVID-19 symptom assessment, vital signs, immunogenicity, PD, PK, coagulation, serum sample for exploratory assessments

The window for the visits following baseline will be constructed in such a way that the upper limit of the interval falls halfway between the two visits (the lower limit of the first post-baseline visit will be Day 2). If an odd number of days exists between two consecutive visits, then the upper limit will be taken as the midpoint value minus 1 day.

One or more results for a particular variable may be obtained in the same visit window. In such an event, the result with the date closest to the expected visit date will be used in the analysis. In the event that two observations are equidistant from the expected visit date, the later observation will be used in the analysis.

The visit windows are defined in the following tables.

Table 3: Analysis windows for serum sample for SARS-CoV-2 serology, ADA and SARS-CoV-2 nAbs levels

Arm A

Visit	Day Relative to First Dose	Visit Window (Study Day)
Day 1	≤ 1	≤ 1
Day 29	29	2 – 60
Day 92	92	61 - 106
Day 121	121	107 - 152
Day 183	183	153 - 197
Day 212	212	198 - 242
Day 274	274	243 - 319
Day 365	365	320 - 410
Day 456	456	≥411 [for serology and SARS-CoV-2 nAbs] 411 – 592 [for ADA assessment]
Day 729 (Follow-up)	729	≥593 [for ADA assessment]

Arm B

Visit	Day Relative to First Dose	Visit Window (Study Day)
Day 1	≤ 1	≤ 1
Day 29	29	2 – 60
Day 92	92	61 - 137
Day 183	183	138 - 197
Day 212	212	198 - 242
Day 274	274	243 - 319
Day 365	365	320 - 410
Day 456	456	≥411 [for serology and SARS-CoV-2 nAbs] 411 – 592 [for ADA assessment]
Day 729 (Follow-up)	729	≥593 [for ADA assessment]

Table 4: Analysis windows for serum sample for AZD7442 PK assessment, NLF sample for mucosal response

Arm A

Visit	Day Relative to First Dose	Visit Window (Study Day)
Day 3	3	2 – 6 [subset of 20 participants, PK and NLF assessment]

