4.2.1.1 Definition

ADA assessments of serum samples will be conducted utilizing a tiered approach (screen, confirm, titer), and ADA data will be collected at scheduled visits shown in Protocol Section 1.3. ADA results from each sample will be reported as either positive or negative. If the sample is positive, the ADA titer will be reported as well. In addition, the presence of neutralizing ADA may be tested for all ADA-positive samples. The neutralizing ADA results will be reported as positive or negative. A participant is defined as being ADA-positive if the participant is ADA evaluable and a positive ADA result is available at any time, including baseline and all post-baseline measurements; otherwise, the participant is defined as ADA negative.

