4.2.1.2 Derivations

The number and percentage of ADA-evaluable participants in the following ADA categories in each treatment group will be determined. The number of ADA-evaluable participants in the treatment group will be used as the denominator for percentage calculation. Note that, ADA responses will be summarized for AZD8895, AZD1061, and AZD7442 separately.

- ADA positive at any visit (at baseline and/or post-baseline). AZD7442 is ADA positive if either AZD8895 or AZD1061 is ADA positive. The percentage of these participants in a population is known as ADA prevalence.
- Treatment-induced ADA positive (ADA negative at baseline and ADA positive at ≥ 1 post-baseline assessment with ADA titer $\geq 2 \times$ MRD [minimum required dilution]). In a situation that one of the components AZD8895 and AZD1061 is treatment-induced ADA positive, and the other component is treatment-boosted

ADA positive (as defined below), AZD7442 will be counted in the worst case (i.e., treatment-induced ADA positive).

- Treatment-boosted ADA positive (baseline ADA titer that was boosted by ≥ 4 -fold following drug administration). AZD7442 is treatment-boosted ADA positive if either AZD8895 or AZD1061 is treatment-boosted ADA positive, except in the situation described in the treatment-induced bullet above.
- Treatment-emergent ADA positive (either treatment-induced ADA positive or treatment-boosted ADA positive). The percentage of these participants in a population is known as ADA incidence.
- ADA positive post-baseline and positive at baseline.
- ADA positive at baseline and not detected post-baseline.
- Treatment-emergent ADA (TE-ADA) persistently positive for AZD8895 and AZD1061, is defined as treatment-emergent ADA positive participants having at least 2 post-baseline ADA positive measurements with titer $\geq 2 \times \text{MRD}$ at least 16 weeks (112 days) between the first and last positive measurement, or an ADA positive result at the last available assessment. AZD7442 is persistently positive if one of AZD8895 and AZD1061 is persistently positive.

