- Treatment-emergent ADA (TE-ADA) transiently positive for AZD8895 and AZD1061, is defined as treatment-emergent ADA positive participants having at least one post-baseline ADA positive measurement with titer $\geq 2 \times \text{MRD}$ and not fulfilling the conditions for TE-ADA persistently positive. AZD7442 is transiently positive if the participant is treatment-emergent ADA positive, but neither AZD8895 nor AZD1061 is not fulfilling persistently positive ADA response.
- Non-treatment emergent ADA positive, defined as participants being ADA positive and not fulfilling the conditions for TE-ADA positive.

In addition, the following ADA category may be summarized.

- Neutralizing ADA (to AZD8895, AZD1061, or AZD7442) positive at any time.

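### AEs by ADA response are counted from first dose under a fixed ADA label, so in participants negative at baseline who later turn positive, AEs before the first positive sample count as AEs in ADA-positive participants

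*SAP*

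**What the plan says.** SAP 4.2.1.3 sets out to examine the effect of ADA on safety by descriptive summaries, where the data permit. The "number of participants with AEs by System Organ Class (SOC) and preferred term (PT) will be provided by ADA response", in the groups "Treatment-emergent ADA positive, non-treatment emergent ADA positive, and ADA negative, and by treatment groups".

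The groups are participant-level labels:

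- SAP 4.2.1.1 calls an evaluable participant ADA positive if "a positive ADA result is available at any time, including baseline and all post-baseline measurements".
- SAP 4.2.1.2 defines treatment-induced ADA as "ADA negative at baseline and ADA positive at ≥ 1 post-baseline assessment with ADA titer" of at least 2 × MRD.
- Treatment-boosted ADA is a "baseline ADA titer that was boosted by" at least 4-fold. Treatment-induced and treatment-boosted together form the treatment-emergent group.
- Non-treatment-emergent positives are "defined as participants being ADA positive and not fulfilling the conditions for TE-ADA positive". That group can hold both participants positive at baseline and participants with only a low-titer positive after baseline.

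Under SAP 4.3.2.1, AEs are recorded from the first IMP dose, and only events before that dose are kept out of the tables. The exposure period also starts at the first dose. SAP 4.2.1.4 and 4.2.1.5 plan no sensitivity or supplementary analysis. SAP 4.2.1.3 plans a listing of AEs in ADA-positive participants by category, without a rule on timing relative to ADA.

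**The concern.** The label uses information from after the events it is meant to explain. Someone who is negative on Day 1 and first positive months later is placed in an ADA-positive column for the whole study, including the months when every sample was negative. No section orders AE onset against ADA detection.

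Length of follow-up adds to this. After early termination, Protocol 1.3 ends follow-up with a visit in place of Day 365 for those last dosed on Day 183, and in place of Day 456 for those last dosed on Day 274. Longer follow-up brings more ADA samples and more time to report an AE, so a crude percentage by ADA group can show an association that only reflects time on study. SAP 4.2.1.3 specifies participant counts and no person-time by ADA group. Applying the exposure-adjusted rate of SAP 4.3.2.1 within each label would not cure this, because its clock starts at first dose and would give the pre-detection time to the positive group.

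At stake is the one table meant to show whether ADA go with hypersensitivity, injection-site or infusion-related reactions, which Protocol 8.3.4 lists as AESIs. It could suggest a link that is not there, or dilute one that is.

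**Working it through.** **The plan's own figure.** The only design figure is the probability of at least one AE in 100 participants at a 3% rate: 1 − 0.97^100 = 0.952, which agrees with the stated 95%. The point does not depend on it.

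**Order of events.**

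1. ADA sampling: Protocol 1.3, Tables 1 and 2, schedule the "Serum sample for AZD7442 ADA assessment (predose on days of IMP administration") on Days 1, 29, 92, 121 (Arm A only), 183, 212, 274, 365 and 456. Day 1 predose is the baseline, and Day 29 is the first scheduled post-dose sample. In "Table 3: Analysis windows for serum sample for SARS-CoV-2 serology, ADA and SARS-CoV-2 nAbs levels" (SAP 3.3.2) the Day 29 window opens on study day 2.
2. AE counting starts at the Day 1 dose (SAP 4.3.2.1).
3. For a baseline-negative participant first positive on day d, all AEs on Days 1 to d − 1 are tabulated as ADA positive. With scheduled samples only, that is at least 28 days (29 − 1 = 28).
4. Day 1 is 1 of 5 planned doses in Arm A and 1 of 3 in Arm B, and it is Arm B's only IV dose. In a baseline-negative Arm B participant, an infusion-related reaction comes before the first scheduled post-dose ADA sample.

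**Size.** The documents give neither AE rates nor ADA onset times, so these are illustrations. Assumptions: constant AE rate, T = 365 days of follow-up.

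- Share of the participant's AEs before detection = (d − 1)/T.
- Probability of at least one AE = 1 − exp(−rate × days/365.25). At an assumed 1 AE per participant-year, counted from Day 1 as planned: 1 − exp(−365/365.25) = 63.2%.
- The last two columns give the share of participants with an AE who count only because of a pre-detection event, for example (63.2 − 39.4)/63.2 = 37.6%.

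| First positive (d) | (d − 1)/365 | At least one AE from day d, 1 per year | Owed only to pre-detection AEs, 1 per year | Same, rates 2 to 0.1 per year |
|---|---|---|---|---|
| Day 29 | 28/365 = 7.7% | 60.3% | 4.6% | 2.6% to 7.3% |
| Day 92 | 91/365 = 24.9% | 52.8% | 16.5% | 10.1% to 24.0% |
| Day 183 | 182/365 = 49.9% | 39.4% | 37.6% | 26.8% to 48.6% |
| Day 274 | 273/365 = 74.8% | 22.3% | 64.8% | 54.2% to 73.8% |

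With 456 days of follow-up the shares in the second column fall to 6.1%, 20.0%, 39.9% and 59.9%.

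**Uncertainty of onset.** Detection is not onset. Scheduled treatment-period samples can be 91 days apart (183 − 92 = 91 in Arm B; 365 − 274 = 91 in both arms), so ADA may be present for up to about that long before the sample that shows them.

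**The case against.** The strongest reply is that this is a secondary, descriptive look, done only where the data permit, with no hypothesis tested (SAP 3.3.4). That stands, and it limits the harm to a misleading comparison.

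A second reply is that timing can be recovered. SAP 4.2.1.3 lists ADA results for the whole Safety Analysis Set and AEs in ADA-positive participants, and SAP 3.3.1 uses study day to show when assessments and events start and stop. A careful reader could probably reconstruct the order for individuals. The listings do not correct the summary table, and they give no comparison rate for ADA-negative time.

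A third reply is that cutting at detection may be wrong in the other direction: a reaction caused by ADA shortly before the detecting sample would be credited to ADA-negative time. That is correct, and it is why a single cut date is not enough.

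A reader might also infer that every AE before Day 29 in any ADA-positive participant precedes ADA. The documents do not support that. ADA are sampled predose on Day 1, and participants positive then already had ADA before any tabulated AE; for boosted participants, early AEs precede only the documented boost. Protocol 8.5.2.1 calls for unscheduled ADA samples when an immune-related AE is suspected, and SAP 3.3.3 lets unscheduled results contribute to the summaries, so a first positive can fall before Day 29.

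**Conclusion.** The point holds for participants who are ADA negative at baseline and positive later: the treatment-induced, and the non-treatment-emergent whose only positives come after baseline. Their AEs before the first positive sample are counted in ADA-positive columns, and no ADA-specific person-time allows for unequal follow-up.

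Under a constant AE rate and 365 days of follow-up, about 8% to 75% of such a participant's AEs would precede detection, for first positives from Day 29 to Day 274. Where in that range the trial falls depends on ADA onset times that the documents do not give. AEs that cluster around the first dose would raise the shares; longer follow-up would lower them.

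It would be wrong to conclude that the primary results are affected. The AE tables by arm and the ADA incidence tables do not use this cross-classification, and no error rate is involved. Only the ADA-by-safety comparison can mislead, but the correction is cheap and worth making.

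**What to change.** Keep the planned table and add the following to SAP 4.2.1.3:

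1. **A table split at detection.** Baseline-negative participants who turn positive contribute AEs and participant-years to ADA-negative status until the first positive sample, and to ADA-positive status from then on. They stay positive afterwards, including when the response is classed as transient. Show exposure-adjusted rates by arm, with a note that one participant can appear under both statuses.
2. **A separate row for baseline-positive participants**, boosted or not. None of their time goes into ADA-negative time.
3. **A repeat with an earlier onset**, set at the day after the last negative sample before the first positive. The two versions bracket the unknown onset.
4. **A flag in the AE listing** showing whether AE onset was before, or on or after, the first positive sample.

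The cost is one derived date, a split of person-time and an extra table with its repeat. No new data are needed. ADA onset will still be known only to an interval, so the two versions should be read together.

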4.2.1.4 Sensitivity Analyses of the Primary Endpoint

No sensitivity analysis will be formed for primary endpoint.

4.2.1.5 Supplementary Analyses of the Primary Endpoint

No supplementary analysis will be formed for primary endpoint.

4.2.1.6 Subgroup Analyses

No subgroup analyses will be formed for primary endpoint.

4.2.2 Secondary Endpoints

4.2.2.1 Pharmacokinetic Data

4.2.2.1.1 Definition

Serum samples will be collected for measurement of serum concentrations of AZD8895 and AZD1061 at scheduled visits as per Protocol Section 1.3. Serum concentrations of AZD7442 is calculated as the sum of AZD8895 and AZD1061. For a subset of 20 participants, samples will be additionally collected at Day 3 and Day 11. Analysis of relevant PK parameters may be performed by the Sponsor and reported in a separate report. Three observations > LLOQ are required as a minimum for a PK parameter to be summarized.

4.2.2.2 SARS-CoV-2 Neutralizing Antibodies

4.2.2.2.1 Definition

Titer and fold ratio in SARS-CoV-2 nAbs will be collected and calculated for each arm and will be summarized at each scheduled visit as per Protocol Section 1.3.

4.2.2.2.2 Derivations

The GMT will be calculated as the antilogarithm of $\Sigma(\log_2 \text{ transformed titer}/n)$, i.e. as the antilogarithm transformation of the mean of the log-transformed titer, where n is the number of participants with titer information. The geometric standard deviation (gSD) for GMT will be calculated as the antilogarithm transformation of the standard deviation of the log-transformed titer. The 95% CI will be calculated as the anti-logarithm transformation of the upper and lower limits for a two-sided CI for the mean of the log-transformed titers.

The fold rise is calculated as the ratio of the post-dose titer level to the pre-dose titer level. GMFR will be calculated as anti-logarithm of $\Sigma (\log_2 \text{ transformed (post-dose titer/ pre-dose titer)}/n)$. The gSD and 95% CIs for GMFR will be calculated similarly to those for GMT.

For each treatment group the correlation and 95% confidence interval between log₂ transformed titers and log₂ transformed serum concentration will be bootstrapped using the mixed model approach proposed by Hamlett, Ryan and Wolfinger (2004).

```
proc mixed data=<data> method=ml covtest asycov asycorr;  
  class <subject> <visit> <response identifier>;  
  model <response> = <response identifier>/ solution  
  ddfm=kr;  
  random <response identifier>/ type=un subject=<subject> v  
  vcorr;  
  repeated <response identifier>/ type=un  
  subject=<visit>(<subject>);  
run;
```

The above mixed model will be fitted separately to each treatment group, where response identifier is a classifier variable for either the log₂ transformed titers or log₂ transformed serum concentrations, and response is the respective value for this variable. Two random effect terms are defined for the two levels of the response classifier for each participant. The repeated statement defines the covariance structure for the residuals for visits nested within participant for each level of the response classifier. Both are given an unstructured covariance.

Data is resampled with replacement 10,000 times at the participant level with equal probability fixing the number of participants in each resample to that of the original dataset. Each duplicate participant selected will be treated as a separate individual. The mixed model is fitted to each sample i and the correlation between log₂ titer and log₂ serum concentration is calculated based on converged models as

$$\hat{\rho}_i = \frac{Cov_{subject(2,1)_i} + Cov_{visit(subject)(2,1)_i}}{\sqrt{((Cov_{subject(1,1)_i} + Cov_{visit(subject)(1,1)_i}) \times (Cov_{subject(2,2)_i} + Cov_{visit(subject)(2,2)_i}))}}$$

where Cov represents the covariance term at participant level (subject) and visit nested within participant [visit(subject)]. The same correlation estimate, $\hat{\rho}$ will be fit to the full data (i.e. not resampling) and the mean bias adjusted factor will be derived as

$$\hat{b} = \frac{\sum_{i=1}^n (\hat{\rho}_i - \hat{\rho})}{n},$$

where n is the number of converged models. The median, 2.5th and 97.5th percentiles will be taken over $\hat{\rho}_i - \hat{b}$ to give the bias-adjusted bootstrapped correlation coefficient and 95% CI. Convergence (%) will be defined as percentage of converged models with respect to the number of bootstraps run. This correlation analysis is based on paired quantifiable records from both PK and nAb samples (on the same sample collection date). Samples from illness visits or samples having values <LLOQ are also to be excluded.

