- Arm A: AZD7442 600 mg IM on Day 1 followed by 300 mg IM Q3M for 12 months (ie, Days 92, 183, 274, and 365)

- Arm B: AZD7442 1200 mg IV on Day 1 followed by 600 mg IM Q6M for 12 months (ie, Days 183 and 365)

The total duration of the study for a participant is 105 weeks (approximately 24 months) for both arms which includes the screening period (up to one week), the treatment period (15 months), and the follow-up period (9 months).

Data Safety Monitoring Board

An independent Data Safety Monitoring Board will provide oversight, to ensure safe and ethical conduct of the study.

Cardiovascular Event Adjudication Committee

An independent cardiovascular (CV) Event Adjudication Committee will provide an independent, external, systematic, and unbiased assessment of de-identified blinded data to systematically evaluate CV events.

Statistical Methods

No statistical hypotheses will be tested. Results will generally be summarized by treatment arm using descriptive statistics: frequency and percentages for categorical variables; number of available observations, mean, standard deviation, median, minimum, and maximum, and quartiles where more appropriate for continuous variables.

The final data readout will occur once all participants have completed the follow-up period (at Month 24) or withdrawn due to premature termination of the study.

Primary Endpoints

- The safety and tolerability of AZD7442 will primarily be assessed by the incidence and exposure adjusted incidence of adverse events (AEs), serious adverse events (SAEs), and adverse events of special interest (AESIs).
- The incidence of antidrug antibodies (ADA) to AZD7442 will be assessed and summarized by number and percentage of participants who are ADA positive. The ADA titer will be summarized with descriptive statistics.

Secondary Endpoints

- Individual AZD7442 (tixagevimab and cilgavimab) serum concentration data will be listed and tabulated, along with descriptive statistics. Appropriate PK parameters may be calculated.
- Descriptive statistics for geometric mean titers (GMTs) and geometric mean fold rise (GMFR) in severe acute respiratory coronavirus-2 neutralizing antibodies will include number of participants, geometric mean, geometric standard deviation, 95% confidence interval, minimum, and maximum.

Sample Size

Approximately 200 participants will be randomized to one of 2 AZD7442 dosing regimens: 100 participants to Arm A and 100 participants to Arm B.

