4.2.2.4.2 SARS-CoV-2 Neutralizing Antibodies

SARS-CoV-2 nAb analysis will be based on actual treatment in nAb Evaluable Analysis Set. Two (2) assays will be used to provide titers for authentic virus and pseudovirus nAb.

If a participant has any protocol deviation which is identified as a record-level exclusion for the immunogenicity analysis in Table 5 of the most recent version of the PDMP, then their SARS-CoV-2 nAb samples collected after the date of deviation will be excluded from the analyses.

Due to the change in dosing schedules between CSP V3.0 (dated 09 December 2022) and CSP V4.0 (dated 06 June 2023), there may be visits with a mixture of participants who received and participants who did not receive IMP in previous visit. Therefore, any SARS-CoV-2 nAb samples from participants who did not receive IMP according to the SoA of CSP V3.0, irrespective of the visit date being before or after the effective date of CSP V4.0, will be excluded from analyses at all subsequent visits.

SARS-CoV-2 nAb assessments scheduled for collection pre-dose, but instead collected post-dose at a visit where dosing is done, will be excluded from the analyses.

For participants who receive a COVID-19 vaccine after the first dose of IMP, data collected after receipt of the vaccine will also be excluded. Furthermore, for participant who receive a positive SARS-CoV-2 RT-PCR (defined in Section 4.2.3.4.1), data collected after infection will also be excluded, except in the case that SARS-CoV-2 nAb samples were collected during an illness visit.

Descriptive statistics for titer and fold rise will include number of participants, geometric mean, geometric standard deviation (gSD), 95% confidence interval (CI), minimum and maximum. This will be reported separately for nAbs collected during treatment period and illness visits (the illness visits where the series corresponds to positive RT-PCR test, as defined in Section 4.2.3.4.1, will be used in the summary).

A scatter plot of log₂ transformed titers with log₂ transformed serum concentration for each treatment arm, along with the bias-adjusted bootstrapped correlation coefficient, 95% CI and convergence (%) (see Section 4.2.2.2.1).

Summaries will also be split by the previous COVID-19 vaccination status (as defined in Section 4.1.5.1). Samples from 2 separate assays will be analysed using the same methods as described here.

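### The titer-concentration correlation model has no visit effect in its mean, so each arm's coefficient mixes the shared dosing time course with participant-level agreement, in proportions that differ by arm

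*SAP*

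**What the plan says.** SAP 4.2.2.2.2 gives the model as SAS code. Titer and concentration are stacked as two responses, and the mean model is "model <response> = <response identifier>/ solution", that is, one constant mean for each. Visit is declared in "class <subject> <visit> <response identifier>" and is otherwise used only to group residuals: "The repeated statement defines the covariance structure for the residuals for visits nested within participant for each level of the response classifier". Participant-level and residual covariances are both unstructured.

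The coefficient adds the two levels in numerator and denominator, "where Cov represents the covariance term at participant level (subject) and visit nested within participant [visit(subject". The arms are handled apart: "The above mixed model will be fitted separately to each treatment group". The bootstrap resamples whole participants.

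The records are defined by "This correlation analysis is based on paired quantifiable records from both PK and nAb samples (on the same sample collection date"; illness visits and values below the LLOQ are left out. SAP 4.2.2.4.2 displays the result as "A scatter plot of log₂ transformed titers with log₂ transformed serum concentration for each treatment arm, along with the bias-adjusted bootstrapped correlation coefficient". SAP 4.2.2.5 plans no sensitivity analysis for the secondary endpoints.

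**The concern.** With a constant mean per response, the model treats a participant's visits as exchangeable replicates. They are points on a profile that dosing drives up and down for everybody. Any movement of mean titer and mean concentration from visit to visit goes into the residual covariance and from there into the coefficient.

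Two readings are then at risk. A high coefficient may be taken to mean that participants with more drug than others at the same visit also have higher titers, when part of it is the common time course. And the two arms' coefficients may be set side by side as a property of the regimens, although the schedules differ. Arm A receives 600 mg IM on Day 1 and then "300 mg IM Q3M for 12 months (ie, Days 92, 183, 274, and 365"; Arm B receives 1200 mg IV on Day 1 and then 600 mg IM on Days 183 and 365 (Protocol 1.1). Because every bootstrap resample carries the same schedule, the interval does not reveal either problem.

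**Working it through.** The documents give no value for this correlation, so there is no figure to reproduce.

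**What the model estimates (balanced data, k visits).** Let S_u be the participant-level covariance matrix, S_e the within-participant covariance around the visit means, and v the 2×2 covariance of the visit means over the k visits. All three are matrices for (titer, concentration).

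- Within-participant mean square: S_e + v·k/(k−1).
- Covariance of participant means: S_u + S_e/k. The profile is common to all, so v does not appear.
- Estimated participant covariance: (S_u + S_e/k) − [S_e + v·k/(k−1)]/k = S_u − v/(k−1).
- Sum of the two levels, as used in the SAP formula: S_u − v/(k−1) + S_e + v·k/(k−1) = **S_u + S_e + v**.

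So v enters numerator and denominator in full. This step needs no assumed figure.

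**Size of v by arm.** From the Protocol: doses and days (1.1), half-life of about 90 days (2.2), and the paired sampling days after Day 1 (1.3, Tables 1 and 2), with samples predose on dosing days. Arm A has Days 29, 92, 121, 183, 212, 274, 365 and 456. Arm B has the same days without Day 121. Assumed, not in the documents: one compartment, IM bioavailability 0.67, absorption half-life 5 days, and log2 titer means moving one-for-one with log2 concentration means.

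Each IV dose contributes dose·exp(−ke·t). Each IM dose contributes 0.67·dose·ka/(ka−ke)·[exp(−ke·t) − exp(−ka·t)], with ke = ln2/90 and ka = ln2/5. The log2 profiles (volume cancels) are:

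- Arm A: 8.39, 7.72, 8.39, 7.72, 8.39, 7.71, 7.71, 7.71; variance 0.106.
- Arm B: 9.92, 9.22, 8.21, 9.15, 8.48, 7.47, 8.23; variance 0.568, about five times Arm A's.

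Over half-lives of 70 to 110 days and bioavailability of 0.5 to 1.0, Arm A runs from 0.06 to 0.20 and Arm B from 0.29 to 1.09. Arm B stays larger throughout, and also when the schedule is cut short at a last dose on Day 183 or Day 274.

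**Effect on the coefficient.** Let r be the within-visit correlation and s_c, s_t the within-visit log2 SDs of concentration and titer (assumed). Then

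rho = (r·s_c·s_t + v) / √[(s_c² + v)(s_t² + v)].

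For r = 0.60 and SDs 0.6/0.9:

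- Arm A: (0.324 + 0.106)/√(0.466 × 0.916) = 0.430/0.653 = 0.66.
- Arm B: (0.324 + 0.568)/√(0.928 × 1.378) = 0.892/1.131 = 0.79.

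| SDs (conc./titer) | r, both arms | Arm A | Arm B |
|---|---|---|---|
| 0.6/0.9 | 0 | 0.16 | 0.50 |
| 0.6/0.9 | 0.60 | 0.66 | 0.79 |
| 0.6/0.9 | 0.80 | 0.82 | 0.88 |
| 0.8/1.3 | 0 | 0.09 | 0.34 |
| 0.8/1.3 | 0.60 | 0.63 | 0.72 |
| 0.8/1.3 | 0.80 | 0.81 | 0.85 |

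Maximum-likelihood fits to simulated data (100 per arm, bioavailability 0.7) agree with the formula at r = 0 and 0.60. Adding response-by-visit means returned −0.01 to 0.01 when the simulated value was 0, and 0.60 to 0.61 when it was 0.60, in both arms.

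**Day 1 in Arm B.** The Day 1 PK sample is taken after the infusion, while the Day 1 titer sample is predose (Protocol Table 2 and its footnotes). Both carry the same date, so the pairing rule accepts them if the titer is quantifiable. Arm A has no Day 1 PK sample. Assume a Day 1 titer 4 log2 units below Day 29, an end-of-infusion concentration twice the profile's initial value, bioavailability 0.7, SDs 0.6/0.9 and r = 0.60. Arm B then gives 0.02 if every participant contributes such a pair and 0.42 if 30% do, both below Arm A's 0.66.

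**The case against.** The strongest reply is that this is a choice of target, not an error. The coefficient annotates a scatter plot that is not restricted to one visit, and an all-visit coefficient describes an all-visit plot. The drug itself neutralizes virus, so titer following dosing-driven concentration is largely the exposure-response signal. No hypothesis is tested (Protocol 9.1), no comparison of the arms' correlations is planned, and by-visit summaries already show the time course. All of this stands, and it is why the planned coefficient should be kept. What it leaves open is that the SAP never says which correlation it means, and nothing planned isolates participant-level agreement.

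A reader might infer that Arm B must look more strongly correlated. The documents do not support that: it holds for post-Day-1 visits under the assumptions above, but same-date Day 1 pairs can reverse it.

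A reader might also treat an interval that excludes zero when r = 0 as a false positive against a nominal 5%. The SAP sets no within-visit null and runs no test, so the interval has no such error rate to exceed.

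Finally, visit adjustment does not make the arms comparable by itself. With slope 1 and titer noise SD 0.6, a concentration SD of 0.4 gives 0.4/√(0.16 + 0.36) = 0.55, and 0.6 gives 0.6/√(0.36 + 0.36) = 0.71, for the same underlying relation. Spread could differ because the loading dose is IM in one arm and IV in the other.

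**Conclusion.** The point holds as a minor improvement to a descriptive secondary analysis. It is certain from the code that the mean model has no visit effect, so the common time course enters the coefficient in full, and the schedules give the arms different amounts of it. The coefficient is valid as an all-visit description. It is not evidence of participant-level agreement, and a difference between arms could come from schedule alone.

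The size is less certain. At a within-visit correlation of 0.60 in both arms, the illustration gives a gap of 0.13 (0.66 against 0.79) at the smaller SDs and 0.09 (0.63 against 0.72) at the larger. At 0.80 the gap falls to 0.06 and 0.04. These figures rest on the assumed SDs, bioavailability, absorption and one-for-one movement of means, and on leaving Day 1 out. The direction of the arm difference is not settled by the documents.

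**What to change.** - Keep the planned coefficient, labelled *across all visits, including the common time course*.
- Beside it, report a visit-adjusted coefficient from the same code, with `<response identifier>*<visit>` added to the right-hand side of the MODEL statement and the bootstrap and correlation formula unchanged.
- Exclude Day 1 pairs in which the titer is predose and the concentration postdose.
- State that neither coefficient alone supports a comparison of arms, because the all-visit value depends on the schedule and the visit-adjusted value depends on each arm's within-visit spread.

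The cost is one model term, one record rule, and one more line of output per arm and assay. The downside is a second, usually lower, coefficient that has to be explained.
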